## **Patient Report Outcome (PRO) and Activity (Chapter 9)**

The PROs and activities are not only collected by on site visit, and please refer to Protocol schedule of activities for further details.

CAT at each planned visits, including phone call visits, will be summarised.

EXACT and E-RS are collected for 2 period of 180 days after baseline and Month 18. Summary of these 2 questionnaires will be based on the mean score during baseline (defined as study D1-D7), Month 1-6 (defined as up to 180 days from study D8) and Month 18-24 (defined as up to 180 days from Month 18 visit).

Daily steps collected by wrist band is used to stands for physical activity measures. Daily steps are collected for 2 period of approximately 30 days after baseline and Month 18. Summary of daily steps will be based on the participants mean steps during baseline (defined as study D1-D7), Month 1 (defined as up to 30 days from study D8) and Month 18 (defined as up to 30 days from Month 18 visit).

HRCT data will be summarised at baseline and the end of study. In addition, for participants who had exacerbation visits (a pre-defined special unscheduled visit happened after exacerbation observed), the HRCT data of these visits will be summarised and compared with baseline and the end of study.

[figure not shown]

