## 2.3. Study Design

## 2.4. Statistical Hypotheses / Statistical Analyses

This study is mainly descriptive with no formal inference associated with the study objectives. Nominal P-value may be provided as reference. 2-sided 95% confidence intervals will accompany all effect estimates.

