**Table 3 CT Scan Data and Imaging Endpoints**

Imaging Analysis Category	Imaging Measures (Description)
Lung density/Emphysema	Perc15 (Corrected for Lung Volume) LAA-950 (Low Attenuation Area-950) DPM_Emphysema
Airway	Average wall thickness (mm) Airway Wall Area (%) Average of major inner diameter (mm) Average of minor inner diameter (mm) Total Airway Count (TAC) Pi10 (Including Pi10All and Pi10Le20)
Gas Trapping	E/I ratio Air Volume DPM_Airtrap (Gas Trapping)

Summary of imaging measures at baseline and Visit 4 (Month 30) will be provided by arm descriptively with 95% CI. Change from baseline will be provided in a same table.

Summary of imaging measures change with exacerbation will be provided in the COPD patients who had CT scan in exacerbation visits. The analysis will be based on events (exacerbations) instead of on patients, i.e., a same patient with 2 exacerbation imaging tests will be analysis as 2 records. Descriptive summary of baseline, exacerbation and the end of study (Visit 4 or early withdrawal) will be provided with 95% CI. Exacerbation visit change from baseline, end of study change compared with exacerbation visit will be provided in a same table with covariates of age, sex and height at baseline.

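### The exacerbation imaging contrasts are not adjusted for elapsed time, so they cannot separate acute change from background progression

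*SAP*

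**What the plan says.** SAP section 12 defines the table this way: "Summary of imaging measures change with exacerbation will be provided in the COPD patients who had CT scan in exacerbation visits". The unit of analysis is the event, so one participant can contribute two records. The contents are given as "Descriptive summary of baseline, exacerbation and the end of study (Visit 4 or early withdrawal) will be provided with 95% CI". The two contrasts and their adjustment are then set out: "Exacerbation visit change from baseline, end of study change compared with exacerbation visit will be provided in a same table with covariates of age". The remaining covariates are the participant's sex and height, also taken at baseline. SAP section 2.2.1 describes the same comparison more briefly: "the HRCT data of these visits will be summarised and compared with baseline and the end of study". Neither place mentions time since baseline, intervals of similar length, or a comparator without an exacerbation scan.

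SAP section 5.5.1 allows the baseline value of a measure as a further covariate in model-based analyses. An earlier part of section 12 tabulates change from baseline to Month 30 by arm. On inference, SAP section 2.4 states: "This study is mainly descriptive with no formal inference associated with the study objectives", and "Nominal P-value may be provided as reference".

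The timing limits come from the protocol's schedule of activities. An exacerbation CT requires more than 14 days since the last study CT. A planned clinic visit must follow a completed exacerbation visit by at least 60 days, and may be moved outside its window for that reason. A month is 30 days.

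**The concern.** The table is introduced as showing change with exacerbation, and the second objective is to characterise exacerbation phenotypes partly through radiological features. The quantity of interest is the acute departure from a participant's own course, and how far it reverses. The planned contrasts measure total change since the previous scan. The study expects that total to be non-zero without any exacerbation, since changes in airway thickness and lung density over follow-up are endpoints in their own right.

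Baseline age, sex and height, and the baseline value if added, are fixed before follow-up starts. They do not represent how long after baseline the exacerbation scan was taken. The result therefore depends partly on when exacerbations happened to occur. Progression in the direction of the acute change inflates the first contrast and masks recovery in the second. The SAP deals with this issue elsewhere: the FEV1 and FVC slope models in section 8.1 use each participant's actual time on study.

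**Working it through.** The documents give no sample size, precision or effect figure for imaging, so there is no stated figure to reproduce.

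**1. Range of the interval.**
- Earliest exacerbation scan: day 15 (more than 14 days after the baseline CT).
- Latest, with Visit 4 on day 900 (30 × 30): 900 − 60 = day 840, month 28.
- Latest, with Visit 4 at the end of its +30-day window: 930 − 60 = day 870, month 29. It is later still if Visit 4 is deferred.

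**2. What each contrast contains.** Let *d* be background change over 30 months (taken as linear), *u* the fraction of follow-up elapsed at the exacerbation scan, *A* the acute change, and *C* the part of it still present at end of study.
- Exacerbation minus baseline = *A* + *d·u*
- End of study minus exacerbation = (*C* − *A*) + *d*(1 − *u*)

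Two mean contrasts cannot determine three unknowns. Take mean *u* = 0.5:

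| Scenario (SD units) | First contrast | Second contrast |
|---|---|---|
| *A* = 0.30, *C* = 0.30, *d* = 0 (lasting change, no progression) | 0.30 + 0 = 0.30 | 0 + 0 = 0 |
| *A* = 0.15, *C* = 0, *d* = 0.30 (transient change, progression) | 0.15 + 0.15 = 0.30 | −0.15 + 0.15 = 0 |

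The planned table is the same for two quite different biological stories.

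**3. Illustrative size.** Assume events spread evenly over days 15 to 870 and end of study at day 900.
- Mean day (15 + 870)/2 = 442.5, so mean *u* = 442.5/900 = 0.49. Individual records run from 15/900 = 2% to 870/900 = 97%.
- With an assumed *d* = 0.3 SD of a scan-to-scan difference, drift is 0.3 × 0.49 = 0.15 in the first contrast and 0.3 × 0.51 = 0.15 in the second.
- If an acute change of 0.3 resolves fully, the second contrast averages −0.3 + 0.15 = −0.15, half the true recovery.
- In simulation with *d* = 0.3 and no acute effect, the nominal 95% CI for the first contrast excluded zero in about 15% of runs with 40 scans, 26% with 80 and 42-44% with 150. With *d* = 0.2 and 40 scans it was 10%; with *d* = 0.5 and 150 scans, 82-83%. All of these inputs are assumptions.

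**4. Which adjustment works.** Interpolating between the participant's baseline and end-of-study scans returns *A* − *C·u*. That is correct if the change resolves (*C* = 0). If it lasts (*C* = *A*), it returns *A*(1 − *u*), about half of *A*. In simulation with a lasting change of 1.0, interpolation gave 0.50. A mixed model with time and a single exacerbation indicator gave 0.51, or 0.57 with 100 participants without exacerbations added. Adding a post-exacerbation indicator recovered both a transient and a lasting change, with an SD of about 0.15 against 0.14 for the raw contrast.

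**The case against.** A reader might infer that the plan tests for an exacerbation effect and attributes ordinary progression to it. The documents do not support that. Section 12 describes a summary with confidence intervals and names no test, section 2.4 disclaims formal inference, and no passage says how the change is to be interpreted. The simulated shares of intervals excluding zero therefore describe a reading that the plan does not prescribe.

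The table also exposes part of the problem. Pure drift moves both contrasts in the same direction, while an acute change that resolves moves them in opposite directions. With linear progression and evenly spread events, a reader could compare the exacerbation mean with the midpoint of the baseline and end-of-study means; in simulation that gave a false signal in 5-6% of runs. This stands, but only under those conditions and for records with all three scans. It also fails for a lasting change in the same way as interpolation. The by-arm Month 30 table gives a rough benchmark, but it pools participants with and without exacerbation scans and is not aligned to event dates.

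Two cautions also stand. The protocol's HRCT text is partly redacted, so any timing rule there cannot be seen; the covariate list in SAP section 12 is readable and contains none. The bundled earlier RAP refers imaging to a visit-based MMRM, which supplies no elapsed-time adjustment for exacerbation scans either.

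**Conclusion.** The point holds as a limitation of a descriptive analysis. Both contrasts are reported without adjustment for an interval that can run from just over 2 weeks to about 28-29 months, so they cannot by themselves separate acute change from background progression. No other readable part of the plan removes this.

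The amount of distortion is unknown. The figure of about 0.15 SD per contrast rests on an assumed 30-month progression of 0.3 SD, linear change and evenly spread events. The scan counts used are also assumed: the sub-cohort plans 250 COPD participants (100 + 100 + 50), and nothing states how many will have an exacerbation scan. The simulations treated records as independent, although a participant may contribute two. This is a cheap improvement, not a flaw that invalidates the study.

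**What to change.** In SAP section 12, keep the raw changes as descriptive columns and add the distribution of the baseline-to-exacerbation interval. Then add one mixed model per inspiratory measure, because exacerbation scans are inspiratory only:

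- **Participants:** all sub-cohort COPD participants, including those with no exacerbation scan, who help to estimate background progression.
- **Scans:** all Visit 1, exacerbation, and Visit 4 or early-withdrawal scans.
- **Fixed effects:** time since Visit 1 (continuous), an exacerbation-scan indicator, a post-exacerbation indicator for later scans, GOLD grade, age, sex and height.
- **Random effect:** participant intercept, which also handles two records from one participant. State how a second exacerbation scan is coded on the two indicators.
- **Report:** the exacerbation coefficient (acute change) and its difference from the post-exacerbation coefficient (recovery), each with a 95% CI and labelled descriptive.

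The cost is SAP wording and one model per measure, with no new scans. State the assumptions beside the results: roughly linear progression and, given GOLD grade, a similar background rate in participants with and without an exacerbation scan. Do not drop the post-exacerbation term or substitute interpolation, since either would understate a lasting change by about half.

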## 13. PHENOTYPIC ANALYSES

The data available at Visit 1 will assist in determination of subject phenotypes in disease manifestation.

Phenotypic analyses COPD patients as well as CB patients. Analysis for phenotypic in this SAP will be descriptive. Potential explanatory analysis will be documented in separate documents.

### 13.1. Phenotypes

Summary of phenotypes in Full and Sub-cohort Population will be provided totally and by GOLD grades, including exacerbator, CMH, significant symptoms and ACO. The summary of phenotype will be performed in COPD patients.

- Exacerbator will be summarized with the following grades: Never, Occasional (1 in previous years), Yearly (1 each year in previous years) and Frequent ( $\geq 2$  more in previous year).
- CMH (Chronic Mucus Hypersecretion) is identified using the SGRQ-C questionnaire, defined by answering cough for most days or several days a week (option 1 **OR** 2 for the “I cough” question) **AND** phlegm for most days or several days a week (option 1 **OR** 2 for the “I bring up phlegm (sputum)” question).
- Significant symptoms will be summarized by CAT score  $\geq 10$  and  $< 10$ .
- ACO is defined as COPD patients that have physician diagnosed asthma  $\leq 40$  years of age. Status of ACO before the age of 18 and between age of 18 and 40 will be provided.

### 13.2. Endotypes

Summary of endotypes in Sub-cohort Population will be provided totally and by (baseline) GOLD grades, including Airflow limitation blood eosinophils and plasma fibrinogen.

- Airflow limitation is defined as GOLD grade increased from baseline, and will be summarized by Yes (GOLD grade increased) and No (GOLD grade remain stable or decreased)
- Blood Eosinophils will be summarized by  $> 300 / \mu\text{l}$  and  $\leq 300 / \mu\text{l}$
- Plasma Fibrinogen will be summarized by  $> 400 \text{ mg/dl}$  and  $\leq 400 \text{ mg/dl}$

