More assessments will be conducted among the 400 Biomarker & Digital sub-cohort participants who will be all recruited only from selected Type A hospitals. The sub-cohort will consist of 50 never smoker healthy control, 100 chronic bronchitis (N never smoker: up to 25), 100 GOLD I (N never smoker: up to 25), 100 GOLD II (N never smoker: up to 25) and 50 GOLD III participants (N never smoker: up to 20). All patient population sizes are approximate and subject to feasibility and the same considerations apply regarding breadth and evenness of spread of severity as apply to the main study cohort.

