| Protocol Activity   | Screen/Baseline | Study visit     |   |                 |   |   |
|---|-----------------|-----------------|---|-----------------|---|---|
|   |                 | X  | - | X  | - |   |
| Monthly CAT   | X  | -               | - | X  | - | - |
| Blood biomarkers (inclusive of serum sRAGE, CC16, IP-10, HbA1c) | X               | -               | - | X               | X | X |
| Sputum cytology                                    | X               | -               | - | X               | X | X |
| Sputum microbiome                                  | X               | -               | - | X               | X | X |

CAT=COPD assessment test, COPD=Chronic Obstructive Pulmonary Disease, HRCT=High-resolution computed tomography, EW=Early Withdrawal, EXACT=EXAceration of COPD Tool; SGRQ-C=St.George's Respiratory Questionnaire for COPD. CAPTURE=COPD Assessment in Primary Care to Identify Undiagnosed Respiratory Disease and Exacerbation Risk

1. Exacerbation visits only apply to subjects included in the Biomarker & Digital sub-cohort. Moderate exacerbations are defined as COPD exacerbations that require either systemic corticosteroids (intramuscular (IM), intravenous, or oral) and/or antibiotics. Severe exacerbations are defined as COPD exacerbations requiring hospitalization or result in death.
2. Informed consent must be conducted at the screen visit prior to performing any study procedures.
3. For COPD participants only;
4. When a trimonthly telephone interview overlaps a clinical visit, the COPD exacerbation assessment, COPD medication and treatment questionnaires will be completed at the clinic visit. A month is defined as 30 days in this study.
5. Data collection of COPD exacerbation assessment, COPD medication and treatment are not required for the healthy control participants.
6. CT scan should only be performed at withdrawal visit if the last study CT performed was more than a year ago. Inspiratory and expiratory HRCT scans are required at Visit 1 and Visit 4, while only inspiratory scan will be conducted on exacerbation visit. The CT scan for an exacerbation visit should only be performed if the last study CT scan performed was more than 14 days.
7. Pre-and post- bronchodilator values of spirometry test will be collected at each site visit.

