GOLD I: 60 exacerbators, GOLD II: 60 exacerbators, GOLD III: 30 exacerbators). Further, a proportion of those who are maintenance inhaler treatment naïve will be recruited, aiming for: 10 participants who are maintenance inhaler treatment naïve will be recruited among exacerbators and non-exacerbators in each GOLD I, II, III groups respectively (Figure 3). All patient population sizes are approximate and allow  $\pm 10\%$  for feasibility.

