### **9.2.9. Biomarker(s)**

#### **9.2.9.1. Blood biomarkers**

Blood samples will be taken at Visit 1 and throughout the study as defined in the Time and Events Table. ([Table 1](#))

- Plasma fibrinogen, hsCRP, total/differential blood cell count measurements and haemoglobin will be conducted at central lab for all participants
- Additional protein analysis will be conducted at central lab for the sub-cohort using validated assays. Analytes chosen will include serum sRAGE, CC16 and IP-10, HbA1c.

The blood biomarker assessments will be conducted according to the study reference manual.

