## 5. CONSIDERATIONS FOR DATA ANALYSES AND DATA HANDLING CONVENTIONS

### 5.1. Number of Participants

A total of 2,000 participants are planned to be enrolled, consisting of 1,700 participants with COPD, 180 with chronic bronchitis but without fixed airflow limitation, and 120 never smoker healthy control. Specifically, COPD subjects will be classified using the GOLD grades I – IV (i.e. mild, moderate, severe and very severe). To better understand the disease progression of early stage COPD, i.e. GOLD I and II grades, COPD participants will be recruited in the following manner: GOLD I: 700, GOLD II: 700, GOLD III: 200, GOLD IV: 100 ([Figure 1](#)[Error! Reference source not found.](#)).

[figure not shown]
Figure 1 Study Population Schematic

More assessments will be conducted among the 400 Biomarker & Digital sub-cohort participants who will be all recruited from selected Type A hospitals. The sub-cohort consists of 50 never smoker healthy control, 100 chronic bronchitis (N never smoker: 25), 100 GOLD I (N never smoker: 25), 100 GOLD II (N never smoker: 25) and 50 GOLD III participants (N never smoker: 20) ([Figure 2 Sub-cohort Population Schematic](#)). In GOLD I-III grades, certain number of COPD participants with previous exacerbation history (i.e. exacerbators) will be recruited (target number of subjects are as follows - GOLD I: 60 exacerbators, GOLD II: 60 exacerbators, GOLD III: 30 exacerbators). Further, a proportion of those who are maintenance inhaler treatment naïve

will be recruited, aiming for: 10 participants who are maintenance inhaler treatment naive will be recruited among exacerbators and non-exacerbators in each GOLD I, II, III groups respectively (Figure 2). All patient population sizes are approximate and allow +/- 10% for feasibility.

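### SAP 13.2 summarises the eosinophil and fibrinogen endotypes only in the sub-cohort, although both markers are measured in every participant

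*SAP*

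**What the plan says.** SAP 13.2 states: "Summary of endotypes in Sub-cohort Population will be provided totally and by (baseline) GOLD grades". It lists three items: airflow limitation (GOLD grade increased from baseline, yes or no), blood eosinophils split at 300/µl, and plasma fibrinogen split at 400 mg/dl.

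The section directly above it, SAP 13.1, takes a wider population: "Summary of phenotypes in Full and Sub-cohort Population will be provided totally and by GOLD grades". SAP Table 2 lists phenotypic analyses, the title of the chapter that contains 13.2, under the Full population as well as the Sub-cohort. SAP 2.1 says that phenotype analyses become descriptive. It does not say that endotypes move to the sub-cohort only.

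On who is measured, Protocol 9.2.9.1 states: "Plasma fibrinogen, hsCRP, total/differential blood cell count measurements and haemoglobin will be conducted at central lab for all participants". The objectives tables in Protocol 4 and SAP 2.2 list fibrinogen and the differential count as main-cohort endpoints. For spirometry, a footnote to the Protocol 2 schedule reads: "Pre-and post- bronchodilator values of spirometry test will be collected at each site visit".

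On the make-up of the sub-cohort, the Protocol synopsis gives 50 healthy controls, 100 chronic bronchitis, 100 GOLD I, then "100 GOLD II (N never smoker: up to 25) and 50 GOLD III participants". There is no GOLD IV target. Protocol 5.2 sets exacerbator targets of "GOLD I: 60 exacerbators, GOLD II: 60 exacerbators, GOLD III: 30 exacerbators".

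**The concern.** The proportion of patients above each cut-off, by GOLD grade, is a natural output for objective 2 (characterising stable disease), and the data for it exist in the whole cohort. As 13.2 is worded, the final report would give it for a small, selected part of the cohort only.

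Three things are lost. The GOLD IV row is empty. The rows for grades I to III rest on a quarter or less of the available participants. The total row describes a group that differs from the cohort:

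- It comes only from selected Type A hospitals, whereas the cohort is recruited 2:1 from Type A and Type B.
- It is aged 50 to 80 rather than 40 to 80, with BMI below 35.
- Ever smokers need at least 10 pack-years rather than at least 1.
- Its COPD members are filled to a target of 60% exacerbators.

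Other tables do not recover these proportions. SAP 10 summarises fibrinogen and blood counts by n, mean, SD, median, range and geometric mean, and the share above a threshold cannot be read from those.

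**Working it through.** **Plan's own figures.** The documents give no precision figure for the endotypes. The group targets add up: 700 + 700 + 200 + 100 = 1,700 COPD; 1,700 + 180 + 120 = 2,000; sub-cohort 50 + 100 + 100 + 100 + 50 = 400. The one single-group interval width in Protocol 10.1.3 concerns FEV1 decline and reproduces: 2 × 1.96 × 125.1 / √1,275 = 13.7 mL/year. It does not bear on this table.

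**Inputs.** Full-cohort COPD by grade I/II/III/IV: 700/700/200/100 (SAP 5.1). Sub-cohort COPD by grade: 100/100/50/0, total 250 (Protocol synopsis, SAP 5.1). Exacerbator target: 60 + 60 + 30 = 150 (Protocol 5.2). Endotype prevalence p is not in the documents, so a range of 10% to 50% is assumed.

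**What the restriction drops.** All COPD: (1,700 − 250)/1,700 = 85.3%. GOLD I and GOLD II: 600/700 = 85.7% each. GOLD III: 150/200 = 75%. GOLD IV: all 100.

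**Change of mix.** The grade shares I/II/III/IV move from 41.2/41.2/11.8/5.9% to 40/40/20/0%. Exacerbators: 150/250 = 60% by target.

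**Attainable precision.** The 95% half-width is 1.96 × √(p(1−p)/n). For example, at p = 0.30 in all COPD it is 1.96 × √(0.21/250) = 5.7 points against 1.96 × √(0.21/1,700) = 2.2 points. The width ratio is √(n full / n sub), whatever p is.

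| Group | n sub / full | Sub-cohort, p = 10 / 30 / 50% | Full, p = 10 / 30 / 50% | Ratio |
|---|---|---|---|---|
| All COPD | 250 / 1,700 | 3.7 / 5.7 / 6.2 | 1.4 / 2.2 / 2.4 | 2.61 |
| GOLD I, GOLD II (each) | 100 / 700 | 5.9 / 9.0 / 9.8 | 2.2 / 3.4 / 3.7 | 2.65 |
| GOLD III | 50 / 200 | 8.3 / 12.7 / 13.9 | 4.2 / 6.4 / 6.9 | 2.00 |
| GOLD IV | 0 / 100 | none | 5.9 / 9.0 / 9.8 | n/a |

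The introduction to SAP 13 also mentions chronic bronchitis patients. Including them gives 350 against 1,880 and a ratio of √(1,880/350) = 2.32.

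These are enrolment numbers and so apply at Visit 1. If the planned 25% dropout applied equally at Visit 4, every half-width would grow by 1/√0.75 = 1.15 and the ratios would not change.

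**The third item.** SAP 8.3 tabulates disease status, including GOLD grade, at each post-baseline visit by baseline arm in the Full Population. Whether a grade rose can be read from that table. A GOLD IV participant cannot move up a grade, so the missing GOLD IV row loses nothing for this item.

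**The case against.** The best case for the plan is that Protocol 5.4 sets up the Biomarker and Digital sub-cohort partly to identify endotypes, so a sub-cohort table follows a stated purpose and the absence of GOLD IV is by design. That is a good reason to keep the sub-cohort table. It is not a reason to leave out the full-cohort one for two markers that the plan itself classes as main-cohort endpoints.

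SAP 2.1 does say in general terms that population definitions follow the SAP. That covers how each population is defined. It does not tell a reader that two main-cohort markers will be summarised in a subset. The earlier RAP bound with the SAP marked both markers for main cohort and sub-cohort in its Table 5. That text is superseded and the difference is not an error, but it shows that the table was once planned in both populations.

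Three further points stand and limit the finding. The analysis is descriptive, with no formal inference, and 13.2 plans no interval, so the half-widths show what the data could support rather than a planned output. The full COPD cohort is itself filled by GOLD quota, so its total row is not a natural prevalence either; the gain is mainly in the rows by grade. And the documents give no expected exacerbator share for the full cohort, so the effect of the 60% target on these proportions cannot be sized. A reader might infer a known bias from the enrichment. The documents support only that the two groups were selected differently.

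**Conclusion.** The point holds for eosinophils and fibrinogen. Both are collected in all participants, the SAP's neighbouring section and its own population table point to the Full population, and no other planned table gives the proportions above the cut-offs. Restricting 13.2 leaves out 85.3% of COPD participants and all of GOLD IV, and makes the attainable intervals for all COPD about 2.6 times wider.

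This rests on planned group sizes, which the documents call approximate (±10%), and on the assumed prevalence range of 10% to 50%. The width ratios do not depend on prevalence.

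Two stronger readings are not supported. A reader might infer that GOLD worsening is also lost outside the sub-cohort; SAP 8.3 shows that it is not. A reader might also compare the 400 sub-cohort members with the 2,000 enrolled ("A total of 2,000 participants are planned to be enrolled, consisting of 1,700 participants with COPD, 180 with chronic bronchitis" and 120 healthy controls). Those totals include people without COPD, and the table by GOLD grade rests on 250 against 1,700.

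Severity is low. No conclusion of the study depends on this table, but the improvement is nearly free.

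**What to change.** In SAP 13.2, specify the Full and Sub-cohort populations for the eosinophil and fibrinogen categories, in line with 13.1 and Table 2. Keep the sub-cohort table alongside, since it serves the aim in Protocol 5.4. For the airflow-limitation item, add a cross-reference to SAP 8.3.

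If the sponsor prefers to keep the restriction, SAP 2.1 should state it and give the reason, and Table 2 should be brought into line.

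The cost is a short wording change and one more run of an existing table on data already collected. No new assessment or derivation is needed.
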